#### **8.4 Events or outcomes not qualifying as adverse events or serious adverse events / Progression / Recurrence of the Disease under study**

An event which is part of the natural course of the disease under study (i.e., disease progression, recurrence) is captured as an efficacy measure; therefore it does not need to be reported as a SAE.

Progression/recurrence of the tumor will be recorded in the clinical assessments in the eCRF. Death due to a progressive disease is to be recorded on a specific form in the eCRF but not as a SAE.

However, if the progression of the underlying disease is greater than that which would normally be expected for the patient, or if the investigator considers that there was a causal relationship between treatment with recMAGE-A3 +AS15 or protocol design/procedures and the disease progression/recurrence, then this must be reported as a SAE.

Any new cancer (non-related to the cancer under study) must be reported as an SAE.

#### **8.5 Clinical Laboratory Parameters and other Abnormal Assessments Qualifying as Adverse Events and Serious Adverse Events**

Abnormal laboratory findings (e.g., clinical chemistry, haematology, urinalysis) or other abnormal assessments that are judged by the investigator to be clinically significant will be recorded as AEs or SAEs if they meet the definition of an AE, as defined in Section 8.1 or SAE, as defined in Section 8.2.

Clinically significant abnormal laboratory findings or other abnormal assessments that are detected during the study or are present at baseline and significantly worsen following the start of the study will be reported as AEs or SAEs as well as individual laboratory values. However, clinically significant abnormal laboratory findings or other abnormal assessments that are associated with the

disease being studied, unless judged by the investigator as more severe than expected for the patient's condition, or that are present or detected at the start of the study and do not worsen, will not be reported as AEs or SAEs.

The investigator will exercise his or her medical and scientific judgement in deciding whether an abnormal laboratory finding or other abnormal assessment is clinically significant.

## **8.6 Detecting and recording adverse events, serious adverse events**

### **Time Period, Frequency, and Method of Detecting Adverse Events and Serious Adverse Events**

All non-serious AEs occurring within the period beginning at the first administration of study treatment and ending 30 days after the last administration of study treatment must be recorded on the Adverse Event form in the patient's eCRF, irrespective of intensity or whether or not they are considered study treatment-related.

All SAEs must be recorded from the first administration of study treatment till the concluding visit (Visit 14, Week 112 or later) and at least 30 days after the last administration of study treatment in the event of early discontinuation of study treatment administration.

Additionally, in order to fulfil international reporting obligations, SAEs that are related to study procedures will be reported from the date of signature of informed consent. However, cystectomy before the first administration of study treatment is not considered as a study procedure. Therefore, foreseeable AEs and SAEs specifically related to the cystectomy prior to first study treatment administration should not be reported. See Section 8.9 for instructions for reporting and recording SAEs.

**Table 9 summarising the periods for AE and SAE reporting during the whole study.**

Study activity	Screening phase	Treatment phase			Concluding visit	
		Visit 1	Visit X (X=2 to 13)	30 days post Visit X		
	From ICF b signature to Visit 1				Visit 14	
Reporting of AEs						
Reporting of SAEs						
Reporting of potential Immune Mediated Diseases						
Reporting of SAEs related to study participation a						
Reporting of SAEs related to study treatment						
Reporting of Pregnancy						

a. Cystectomy is not considered as study procedure; SAEs related to this surgery should not be recorded.

b. **ICF for study participation**

All AEs either observed by the investigator or one of his clinical collaborators or reported by the patient spontaneously or in response to a direct question will be evaluated by the investigator. AEs not previously documented in the study will be recorded in the Adverse Event form within the patient's eCRF. The nature of each event, date and time (where appropriate) of onset, outcome, intensity and relationship to study treatment administration should be established. Details of any corrective treatment should be recorded on the appropriate page of the eCRF. Refer to Section 6.6. As a consistent method of soliciting AEs, the patient should be asked a non-leading question such as: "Have you felt different in any way since receiving the treatment or since the previous visit?" N.B. The investigator should record only those AEs having occurred within the time frame defined above.

AEs already documented in the eCRF, i.e. at a previous assessment, and designated as "not recovered/not resolved" or "recovering/resolving" should be reviewed at subsequent visits, as necessary. If these have resolved, the documentation in the eCRF should be completed.

When an AE/SAE occurs, it is the responsibility of the investigator to review all documentation (e.g., hospital progress notes, laboratory, and diagnostics reports) relative to the event. The investigator or designate will then record all relevant information regarding an AE/SAE in the

eCRF and on the SAE Report Forms. It is not acceptable for the investigator to send photocopies of the patient's medical records to the Sponsor in lieu of the appropriate completed AE/SAE pages in the eCRF and SAE Report Form. However, there may be instances when copies of medical records for certain cases are requested by the Sponsor. In this instance, all subject identifiers will be blinded on the copies of the medical records prior to submission to the Sponsor.

Paper SAE Report Forms and the facsimile (fax)/e-mail system will be the primary modes for reporting SAEs to the Sponsor during the study period. SAEs should also be reported on the SAE screens in the electronic system.

The investigator will attempt to establish a diagnosis of the event based on signs, symptoms, and/or other clinical information. In such cases, the diagnosis should be documented as the AE/SAE and not the individual signs/symptoms.

## **8.7 Evaluating Adverse Events and Serious Adverse Events**

### **8.7.1 Assessment of intensity**

Severity of AEs will be assessed according to the International Common Terminology Criteria for Adverse Events (CTCAE); version 4.0; Appendix 4.

The investigator will make an assessment of intensity for all AEs, including SAEs reported during the study. The assessment will be based on the investigator's clinical judgment. The intensity of each AE and SAE recorded in the Adverse Event form within the patient's eCRF, SAE screens in the eCRF and SAE Report Form should be assigned according to the table given in the CTCAE (Version 4.0; Appendix 4).

An AE that is assessed as Grade 3 (severe) should not be confused with an SAE. Grade 3 is a category utilized for rating the intensity of an event; and both AEs and SAEs can be assessed as Grade 3. An event is defined as 'serious' when it meets the definition in Section 8.2.

### **8.7.2 Assessment of causality**

The investigator is obligated to assess the relationship between the investigational product and the occurrence of each AE/SAE. The investigator will use clinical judgement to determine the relationship. Alternative causes, such as natural history of the underlying diseases, concomitant therapy, other risk factors and the temporal relationship of the event to the investigational product will be considered and investigated. The investigator will also consult the Investigator Brochure and/or Product Information, for marketed products, in the determination of his/her assessment.

There may be situations when a SAE has occurred and the investigator has minimal information to include in the initial report to the Sponsor. However, it is very important that the investigator always makes an assessment of causality for every event prior to submission of the SAE to the Sponsor. The investigator may change his/her opinion of causality in light of follow-up information, amending the SAE information accordingly. The causality assessment is one of the criteria used when determining regulatory reporting requirements.

In case of concomitant administration of multiple treatments, it may not be possible to determine the causal relationship of general AEs to the individual treatments administered. The investigator should, therefore, assess whether the AE could be causally related to study treatment administration rather than to the individual treatments.

Causality of all AEs should be assessed by the investigator using the following question: Is there a reasonable possibility that the AE may have been caused by the investigational product ?

NO : The AE is not causally related to administration of the study treatment. There are other, more likely causes and administration of the study treatment is not suspected to have contributed to the AE.

YES : There is a reasonable possibility that the treatment contributed to the AE.

Non-serious and serious AEs will be evaluated as two distinct events. If an event meets the criteria to be determined “serious” (see Section 8.2 for definition of serious adverse event), it will be examined by the investigator to the extent to be able to determine ALL contributing factors applicable to each serious adverse event.

Other possible contributors include:

- Medical history
- Other medication
- Protocol required procedure
- Other procedure not required by the protocol
- Erroneous administration
- Other cause (specify).

## **8.8 Follow-up of Adverse Events and Serious Adverse Events and Assessment of Outcome**

After the initial AE/SAE report, the investigator is required to proactively follow each patient and provide further information to the Sponsor on the patient's condition. All AEs and SAEs documented at a previous visit/contact and designated as not recovered/not resolved or recovering/resolving will be reviewed at subsequent visits/contacts.

Investigators will follow-up patients:

- with SAEs or patients withdrawn from the study as a result of an AE, until the event has resolved, subsided, stabilized, disappeared, the event is otherwise explained, or the patient is lost to follow-up; or
- in the case of other non-serious AEs, until they complete the study or they are lost to follow-up.

Clinically significant laboratory abnormalities will be followed up until they have returned to normal, or a satisfactory explanation has been provided. Additional information (including but not limited to laboratory results) relative to the subsequent course of such an abnormality noted for any patient must be made available to the Study Monitor.

The Sponsor may request that the investigator perform or arrange for the conduct of supplemental measurements and/or evaluations to elucidate as fully as possible the nature and/or causality of the AE or SAE. The investigator is obliged to assist. If a patient dies during participation in the study or during a recognized follow-up period, the Sponsor will be provided with a copy of any available post-mortem findings, including histopathology. New or updated information will be recorded on the paper SAE Report Form as well as on the originally completed SAE screens in eCRF. The paper SAE Report Forms should be re-sent by facsimile (fax)/e-mail system to the Sponsor within 24 hours of receipt of the follow-up information as outlined in Section 8.9.1. Refer to Section 8.9.2 for details of the reporting system.

Outcome of any non-serious AE occurring within 30 days post-administration or any SAE reported during the entire study will be assessed as:

- Recovered/resolved
- Not recovered/not resolved
- Recovering/resolving
- Recovered with sequelae/resolved with sequelae
- Fatal (SAEs only).

## **8.9 Prompt Reporting of Serious Adverse Events to the Sponsor**

The paper SAE Report Forms and the facsimile (fax)/e-mail system will be the primary modes for reporting SAEs to the Sponsor during the study period. SAEs should also be reported on the SAE screens in the electronic system.

### **8.9.1 Time frames for submitting serious adverse event reports to the Sponsor**

SAEs will be reported promptly to the Sponsor once the investigator determines that the event meets the protocol definition of an SAE. The investigator or designate will complete and submit relevant information on the paper SAE Report Forms and fax or e-mail the (scanned) SAE reports to the Sponsor **WITHIN 24 HOURS OF HIS/HER BECOMING AWARE OF THESE EVENTS**. Additional or follow-up information relating to the initial SAE report is also to be completed and submitted on the paper SAE Report Forms and faxed/e-mailed to the Sponsor within 24 hours of receipt of such information.

During the study, the investigator should also enter and update the SAE information in the SAE screens in eCRF.

### **8.9.2 Completion and transmission of serious adverse event reports to the Sponsor**

Once an investigator becomes aware that a SAE has occurred in a study patient (including a screened patient), the investigator or designate will complete and submit the information on the paper SAE Report Forms and fax/e-mail the SAE reports to the Sponsor within 24 hours as outlined in Section 8.9.1. The paper SAE Report Forms will always be completed as thoroughly as possible with all available details of the event, signed by the investigator or designate and faxed to the Sponsor. If the investigator or designate does not have all information regarding an SAE, he/she will not wait to receive additional information before notifying the Sponsor of the event and faxing the SAE Report Forms. The SAE Report Forms should be updated when additional information is received and faxed/e-mailed to the Sponsor **WITHIN 24 HOURS** as outlined in Section 8.9.1.

The investigator will always provide an assessment of causality at the time of the initial report as described in Section 8.7.2.

NB. An event which is part of the natural course of the disease under study (i.e., disease recurrence) is captured in the study as an efficacy measure; therefore it does not need to be reported as an SAE (see Section 8.4).

In rare circumstances, in the absence of facsimile/e-mail equipment for reporting SAEs (**including deaths determined by the investigator to be related to treatment administration**), notification by telephone is acceptable, with a copy of the SAE Report Form sent by mail. Initial notification via the telephone does not replace the need for the investigator or designate to complete and sign the SAE Report Forms and fax/e-mail the SAE form to the Sponsor.

In the event of a death determined by the investigator to be related to study treatment administration, sending of the fax must be accompanied by telephone call to the Study Contact for Reporting SAEs.

## 8.10 Regulatory Reporting Requirements for Serious Adverse Events

The investigator will promptly report all SAEs to the Sponsor in accordance with the procedures detailed in Section 8.9. The Sponsor has a legal responsibility to promptly notify, as appropriate, both the local regulatory authority and other regulatory agencies about the safety of a product under clinical investigation. Prompt notification of SAEs by the investigator to the Study Contact for Reporting SAEs is essential so that legal obligations and ethical responsibilities towards the safety of other patients are met.

The investigator, or responsible person according to local requirements, will comply with the applicable local regulatory requirements related to the reporting of SAEs to the IRB/IEC and, if required, to the applicable government authority.

Investigator safety reports are prepared according to the current Sponsor's policy and are forwarded to investigators as necessary. An investigator safety report is prepared for a SAE(s) that is both attributable to investigational product and unexpected (SUSAR). The purpose of the report is to fulfil specific regulatory and Good Clinical Practice (GCP) requirements, regarding the product under investigation.

An investigator who receives an investigator safety report describing a SAE(s) or other specific safety information (e.g., summary or listing of SAEs) from the Sponsor will file it with the Investigator Brochure or other appropriate study documentation and will notify the IRB or IEC, if appropriate according to local requirements.

## **8.11 Post-study Adverse Events and Serious Adverse Events**

A post-study AE/SAE is defined as any event that occurs outside of the AE/SAE detection period defined in Section 8.6. Investigators are not obligated to actively seek AEs or SAEs in former study participants.

However, if the investigator learns of any SAE, including a death, at any time after a patient has been discharged from the study, and he/she considers the event reasonably related to the investigational product, the investigator will promptly notify the Study Contact for Reporting SAEs. The investigator or designate should use the paper SAE Report Forms and the facsimile (fax)/e-mail system if SAE follow ups or new SAEs have to be reported.

## **8.12 Pregnancy**

Patients who become pregnant during the study treatment phase must not receive additional doses of study treatment but may continue other study procedures at the discretion of the investigator.

The investigator, or his/her designee, will collect pregnancy information on any patient who becomes pregnant while participating in this study i.e. from signature of first informed consent till the concluding visit , or till recurrence/death if occurring before the the concluding visit . The investigator, or his/her designee, will record pregnancy information on the Pregnancy Report Form and submit it to the Sponsor within 24 hours of learning of a patient's pregnancy. The patient will be followed to determine the outcome of the pregnancy. At the end of the pregnancy, whether that be full-term or prematurely, information on the status of the mother and child will be forwarded to the Sponsor. Generally, follow-up will be no longer than 6 to 8 weeks following the estimated delivery date.

While pregnancy itself is not considered an AE or SAE, any pregnancy complication or elective termination of a pregnancy for medical reasons will be recorded as an AE or a SAE, as described in Section 8.1 and 8.2, and will be followed as described in Section 8.8.

A spontaneous abortion is always considered to be a SAE and will be reported as described in Section 8.8. Furthermore, any SAE occurring as a result of a post-study pregnancy AND considered reasonably related in time to receipt of the investigational product by the investigator, will be reported to the Sponsor as described in Section 8.11. While the investigator is not obligated to actively seek this information from former study participants, he/she may learn of a pregnancy through spontaneous reporting.

Information on pregnancies identified during the screening phase/prior to treatment administration does not need to be collected; this information need not be administered in the eCRF.

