### 5.2 Inclusion Criteria

To be eligible for this study, patients needed to meet all of the following inclusion criteria:

1. Aged greater than or equal to 18 years at the time ICF is signed, either sex.
2. Histologically confirmed (after cystectomy or if needed transurethral resection) urothelial carcinoma of the bladder which is MAGE-A3 positive.
3. Written informed consent for tissue sampling, the mandatory analyses and for the complete study has been obtained prior to the performance of any other protocol-specific procedure.
4. TNM classification at pathological examination of surgically removed specimen: Stage T2,3 N0 or N1 or N2 and M0 disease or Stage T4 N0 M0 disease. (TNM classification see Appendix 3)
5. The patient is free of residual disease and free of metastasis, as confirmed by a negative baseline Computer Tomogram (CT scan) or Magnetic Resonance Imaging (MRI) of the pelvis, abdomen and chest no more than 13 weeks prior to randomization. Other examinations should be performed as clinically indicated.
6. Patient is fully recovered from surgery within 13 weeks following cystectomy. For patients who receive adjuvant chemotherapy, the patient is fully recovered within 3-6 weeks following chemotherapy.
7. The patient must have adequate bone-marrow reserve, defined as an absolute neutrophil count  $\geq 1.0 \times 10^9/L$ , and a platelet count  $\geq 75 \times 10^9/L$ , adequate renal function, defined as a

serum creatinine  $\leq$  1.5 times the Upper Limit of Normal (ULN), and adequate hepatic function, defined as a Total bilirubin  $\leq$  1.5 times the ULN, and a Alanine transaminase (ALAT) and Aspartate Transaminase (ASAT)  $\leq$  2.5 times the ULN as assessed by standard laboratory criteria.

8. World Health Organization (WHO) performance status 0 – 1 at the time of randomization. (Appendix 2)
9. If the patient is female, she must be of non-childbearing potential, i.e. have a current tubal ligation, hysterectomy, ovariectomy or be post menopausal, or if she is of childbearing potential, she must practice adequate contraception (definition see Section 7.3.1) for 30 days prior to administration of study treatment, have a negative pregnancy test and continue such precautions during all study treatment period and for 2 months after completion of the injection series.

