## 7. STUDY ASSESSMENTS AND PROCEDURES

### 7.1 General Study Aspects

#### Attendance for study visits

It is the investigator's responsibility to ensure that the intervals between visits/contacts are strictly followed.

Patients will be required to attend for study treatment administration and assessment according to the schedule shown below (Section 7.2). The first study treatment will take place maximum 7 days after randomization. Permitted deviation from the stipulated date of each visit (due e.g. to weekends or public holidays) will be as follows:

Screening 1:	prior to or shortly after cystectomy
Screening 2:	
For patients not receiving adjuvant chemotherapy	max 13 weeks after cystectomy
For patients receiving adjuvant chemotherapy	within 3-6 weeks after the last day of chemotherapy administration
Visit 1:	max 7 days after randomization and max 36 weeks after cystectomy
Visits 2-5:	± 4 calendar days.
Visits 6-13:	± 14 calendar days.

The concluding visit will take place at least 30 days after the patient's last dose of study product.

The follow-up visits planned in the initial study protocol has been cancelled.

Any deviation greater than this will be regarded as a protocol violation.

In each case, the sponsor will decide, if appropriate in consultation with the IDMC, whether the violation is to be regarded as:

- A minor violation (i.e., without consequence),
- A major violation (resulting in exclusion of the patient from the population of patients evaluable according to protocol (ATP)).

When the permitted deviations are applied or when a study treatment has to be postponed (refer to Section 6.3.2.1 for details on postponement of study treatment), the next study visit should be planned at a time allowing:

- A minimum of 14 days between 2 treatment administrations,
- To keep up with the schedule as based on the date of first study treatment administration (Visit 1).

*During the treatment phase, 1 week equals 7 calendar days. During the treatment phase timings will be counted in weeks.*

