study will continue only with patients from the active treatment group who will decide to stay in the study. Signature of the ICF addendum will be documented in eCRF at visit S2.

These visits will take place at 12-weekly intervals i.e. at time points 24, 36, ...108 weeks after V1, with a permitted deviation of up to 14 days.

During Visit 6 to Visit 13 the following procedures will be performed:

- Recording of concomitant medication (each visit)
- Recording of (serious) adverse events and potential Immune-Mediated Diseases (each visit)
- Routine physical examination including WHO performance status assessment (each visit)
- Cross-sectional imaging or Magnetic Resonance Imaging (CT scan or MRI of chest, abdomen and pelvis) (each visit)
- Pregnancy test (each visit)

A pregnancy test will be repeated every 3 months for females of childbearing potential and should be performed at any time during the study for all women of childbearing potential if the investigator or patient suspects that pregnancy has occurred while the subject was being treated on protocol therapy.

- Blood sampling for safety at V8, and V12

Note that as of Protocol Amendment 4.0, Smoking status (V6, V8, V10, V12), blood sampling for immunological examination (at V7, V8 and V10) and urine sampling (at the time of recurrence of bladder cancer in the urinary urothelium, for analysis of MAGE A3 expression, optional, if patient specifically consents to this), as mentioned in the original protocol, will not be performed anymore.

Before each administration the criteria for permanent stopping or postponement of study treatment (Sections 6.3.2.1 and 6.3.2.2) will be checked. If any of these is met, the patient will be withdrawn from study treatment or the administration of study treatment will be postponed.

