#### Visit 14: Concluding visit

This visit will take place at least 30 days after V13, approximately 120 weeks after first administration (V1) with a permitted deviation of up to 14 days, or in case of recurrence or early withdrawal.

The following procedures will be performed:

- Recording of concomitant medication
- Recording of (serious) adverse events and potential Immune-Mediated Diseases
- Routine physical examination including WHO performance status assessment
- Cross-sectional imaging or Magnetic Resonance Imaging (CT scan or MRI of chest, abdomen and pelvis)
- Pregnancy test

A pregnancy test will be repeated every 3 months for females of childbearing potential and should be performed at any time during the study for all women of childbearing potential if the investigator or patient suspects that pregnancy has occurred while the subject was being treated on protocol therapy.

- Blood sampling for safety

Note that as of Protocol Amendment 4.0, Smoking status and blood sampling for immunological examination (optional, if patient specifically consents to this), as mentioned in the original protocol, will not be performed anymore.

As of Protocol Amendment 4.0 the follow-up visits have been cancelled.

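### Section 8.12 can end pregnancy reporting before the 2-month contraception period in inclusion criterion 9 is over, so an uncomplicated exposed pregnancy may go unreported

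*Combined protocol and SAP*

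**What the plan says.** Section 8.12 wants a pregnancy sent to the sponsor within 24 hours and followed to its outcome. The collection window is "from signature of first informed consent till the concluding visit , or till recurrence/death if occurring before the the concluding visit". No minimum time since the last dose is attached to the recurrence cut-off.

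Inclusion criterion 9 (Section 5.2) requires women of childbearing potential to use contraception before treatment and to "continue such precautions during all study treatment period and for 2 months after completion of the injection series".

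The concluding visit (Visit 14) is timed in more than one way:

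- Section 7.1: "The concluding visit will take place at least 30 days after the patient's last dose of study product". The synopsis and Section 4 agree.
- Section 8.6: SAEs are recorded "till the concluding visit (Visit 14, Week 112 or later"). Table 5 and Section 9.1 also use week 112.
- Section 7.3.2, Visit 14: "at least 30 days after V13, approximately 120 weeks after first administration (V1"), with a 14-day allowance, or at recurrence or early withdrawal.

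The last dosing visits are "at time points 24, 36, ...108 weeks after V1", so Visit 13 is at week 108.

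After the study, Section 8.12 still asks for any SAE arising from a pregnancy if the investigator considers it reasonably related in time to the product, but places no duty on the investigator to look for it.

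On the start of the window, the opening rule in 8.12 is collection "from signature of first informed consent till the concluding visit", while its last paragraph says: "Information on pregnancies identified during the screening phase/prior to treatment administration does not need to be collected".

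**The concern.** The contraception requirement and the pregnancy-reporting window serve related purposes, and a reader would expect the second to be at least as long as the first. Here it can be shorter. A site that follows 8.12 exactly could learn of a pregnancy that began within 2 months of the last injection and have no duty to report it, because the concluding visit or a recurrence had already closed the window. The outcome of an exposed pregnancy would then be lost to the safety database.

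The rule is live. Under Amendment 4.0, active-arm patients may go on being dosed until 30 November 2016, and the follow-up visits that might have picked up a later pregnancy have been cancelled. Section 8.6 gives SAEs a floor of at least 30 days after the last dose when treatment stops early; 8.12 gives pregnancies no such floor at recurrence.

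**Working it through.** The plan gives no figure of its own to reproduce; the check is calendar arithmetic.

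**Inputs.** Contraception period: 2 months after the injection series (criterion 9), which is 59 to 62 days over all start dates in 2015 and 2016. Last scheduled dose: week 108 (Section 7.3.2). Concluding visit: each of the three stated timings.

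**Formula.** Uncovered days = length of 2 months minus days from last dose to the end of collection, with a floor of 0.

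**Patients without recurrence.**

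- 30-day minimum: 59 − 30 = 29 to 62 − 30 = 32 days. This minimum also governs patients who stop treatment early.
- Nominal week 112: (112 − 108) × 7 = 28 days after the last dose; 59 − 28 = 31 to 62 − 28 = 34 days. This nominal timing is itself 2 days short of the 30-day minimum.
- About week 120: (120 − 108) × 7 = 84 days, or 70 to 98 days with the 14-day allowance. All exceed 62, so 0 days.

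Example: a dose on the last permitted day, 30 November 2016, allows a concluding visit on 30 December 2016. The contraception period ends on 30 January 2017, 31 days later.

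**Patients with recurrence.** Collection stops at recurrence, so the uncovered time is 59 to 62 days minus the days since the last dose.

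- Visit 5 scan: week 12 against dose 4 at week 9, so 21 days. Uncovered: 59 − 21 = 38 to 62 − 21 = 41 days. The footnotes to Table 4 allow procedures up to 14 days before the visit. A scan then falls 21 − 14 = 7 days after dose 4 and leaves 52 to 55 days.
- Scheduled scans from Visit 6 on: visits are 12 weeks (84 days) apart and the scan precedes the injection. Nominally it falls 84 − 14 = 70 to 84 days after the previous dose, so 0 days are uncovered. Visit windows can shorten this: if the previous dose was 14 days late, 70 − 14 = 56 days, leaving 3 to 6.
- Unscheduled symptomatic relapse: any interval since the last dose is possible, so up to about 2 months.

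**How many women.** The documents give no sex split for the trial. I assume the male-to-female ratio of 3.8:1 in Section 2.1 and the 2:1 allocation apply to the 83 patients randomized when recruitment was put on hold; a few more could be randomized until 3 February 2015. Active arm: 83 × 2/3 ≈ 55. Women: 55 / 4.8 ≈ 12. The share of childbearing potential is not given; assuming 0 to 10% gives 0 to 1.2, so about 0 to 1.

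**The case against.** The strongest reply is that the gap may not exist for patients who complete treatment. Thirty days is a minimum, Section 8.6 says week 112 or later, and Section 7.3.2 puts the visit at about week 120, by which time 2 months have passed. This stands for completers if week 120 is the operative timing. It does not settle the matter, because Table 5 and Sections 8.6 and 9.1 use week 112, and early stoppers fall under the 30-day minimum in any case.

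Second, a reader might infer that patients who relapse generally lose nearly all coverage. The scan schedule does not support that: from Visit 6 on, a relapse found on a scheduled scan nominally comes after the 2 months are over. A large gap needs an unscheduled relapse or the Visit 5 scan.

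Third, there is a backstop. Sections 8.11 and 8.12 keep related post-study SAEs reportable, and 8.12 always counts a spontaneous abortion as an SAE. But this route is passive, and it does not reach an uncomplicated pregnancy.

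Fourth, criterion 9 sets a contraception duration. It does not declare a period of fetal risk, and no section says that reporting must match it. That is fair: aligning the two is sensible drafting, not a rule that the protocol breaks.

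Finally, it is tempting to count the screening-period wording as a further cause of missed pregnancies. It is not. A pregnancy identified before the first dose is unexposed. One that began after consent but is found after dosing still falls under the opening rule of 8.12.

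**Conclusion.** The mismatch is real but limited. Pregnancy collection can close with 29 to 34 days of the contraception period still to run when the concluding visit is held at the 30-day minimum or nominal week 112. It closes with none outstanding at about week 120. Recurrence found soon after a dose can leave most of the 2 months uncovered under any of these timings. What is lost is the report of an uncomplicated exposed pregnancy; serious events remain partly protected.

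The documents do not support the stronger statement that about half of the period is uncovered for every patient, because they contradict themselves on when the concluding visit takes place. The headcount rests on a borrowed population sex ratio and an assumed 0 to 10% of childbearing potential, and comes to about 0 to 1 woman. The point is minor and touches safety reporting only. The conflict over the start of collection is a separate wording defect.

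**What to change.** - Reconcile Section 8.12 with criterion 9, so that pregnancy reporting runs at least to the end of whatever contraception period criterion 9 keeps, counted from the last dose and not ended by recurrence. This leaves the length of that period to the sponsor.
- Reconcile the week 112 statements (Table 5, Sections 8.6 and 9.1) with the week 120 statement in Section 7.3.2.
- Check that the pregnancy row of Table 9 agrees with the revised text. Its content could not be read in the copy reviewed, so no error is claimed there.
- Separately, as wording only: make the start of collection in 8.12 consistent with its last paragraph on pregnancies identified before treatment.

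The cost is a few sentences, a check of one table row, and one later contact for the very few women of childbearing potential.
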